## 17.0 Safety Analyses

### 17.1 Safety Variables

- AEs
- Clinical Laboratory Evaluations
  - Clinical Chemistry
  - Hematology
  - Urinalysis
  - Myocyte Biomarkers
- Vital Signs
  - Supine Blood Pressure
    - Systolic Blood Pressure
    - Diastolic Blood Pressure
  - Pulse rate

- Oral body temperature
- Electrocardiograms (ECG)
  - Heart Rate
  - PR Interval
  - QRS-Duration
  - QT Interval
  - QTc (Frederica) Interval
  - T-Waves
  - U-Waves
- Echocardiograms
  - PAAT
  - RVOT-VTI
  - Inferior Vena Cava Diameter (IVC)
  - Right Atrial Size
  - Right-Ventricular Index of Myocardial Performance (RIMP)
  - Right Ventricle (RV): End-Systolic Pressure
  - RV: End-Diastolic Pressure
  - Tricuspidal Regurgitation
  - Systolic PAP
  - Pulmonary Valve Regurgitation
  - Diastolic PAP
  - Right Ventricular Wall Thickness
  - Right Ventricular Size
  - LVEF
  - Left Ventricular Wall Thickness
  - Ratio of Transmitral Doppler Early Filling Velocity (E) To Tissue Doppler Early Diastolic Mitral Annular Velocity (E')
  - Aortic Valve Insufficiency
  - Mitral Valve Regurgitation
  - Number of subjects per treatment with mPAP exceeding 25 mm Hg
- Physical Examination
- Columbia-Suicide Severity Rating Scale (C-SSRS)

### 17.1.1 Adverse Events

Treatment emergence will be evaluated for all AEs. Treatment-emergent adverse events (TEAE) are those which occur after the first dose of study drug.

TEAEs occurring following dosing in a specific period but before dosing in the next period will be attributed to the treatment in that period. If the time is missing for an AE on a dosing day then the AE will be attributed to the treatment given on that day.

The following missing data will be imputed as defined (for calculations only / will not be presented):

- Missing AE start and / or end times for the calculation of onset and duration will be assumed to be at 00:01 for a start time and 23:59 for end times
- Missing AE severity or relationship will be assumed to be severe or related, respectively
- Missing AE start times for the determination of treatment emergence will be assumed to occur after treatment unless partial date documents the AE as happening prior to treatment
- Missing AE start times for the determination of treatment assignment will be assumed to occur after treatment on the recorded date one minute after dosing
- Missing AE start date will be assumed to be after treatment for the determination of TEAE but will not be attributed to a specific treatment

A summary of number and percentage of subjects reporting TEAEs, TEAEs by severity and relationship, serious AEs (SAEs), and subjects who discontinued study drug due to an AE will be provided.

A summary of the number and percentage of subjects reporting each TEAE, categorized by system organ class and preferred term coded according to the Medical Dictionary for Regulatory Activities (MedDRA), will be presented by treatment and overall. Counting will be done by subject only, not by event; subjects will only be counted once within each body system or preferred term.

A summary of the number and percentage of subjects reporting each TEAE will be presented by relationship to study drugs (as recorded on the eCRF) and by treatment and overall. Subjects with multiple events within a system organ class or preferred term will be counted under the category of their most drug-related event within that system organ class or preferred term.

A summary of the number and percentage of subjects reporting each TEAE will be presented by severity (as recorded on eCRF) and by treatment and overall. Subjects with multiple events within a system organ class or preferred term will be counted under the category of their most severe event within that system organ class or preferred term.

A summary presenting the preferred terms for the events in descending order of frequency for the overall treatment group will also be presented.

All AEs (including non-treatment-emergent events) recorded on the eCRF will be listed by subject.

A separate listing of AEs leading to study drug discontinuation will be provided.

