3.3.1.2 Moxifloxacin

The study will utilize moxifloxacin (400 mg) as a positive-control to assure the study as designed will be able to detect potential ECG effects of balovaptan. Moxifloxacin, a fluoroquinolone antibiotic, when utilized at its recommended therapeutic dose of 400 mg qd is associated with QT prolongation. Regulatory authorities have recommended moxifloxacin as a positive control to evaluate the sensitivity of clinical studies designed to detect small but significant increases in QT interval measurements. Subjects will receive 400 mg oral moxifloxacin in a nested cross-over fashion using a joint placebo/positive control period. In this period, half of the subjects will be dosed with moxifloxacin on Day 2 and the other half dosed on Day 15. To keep the blind between balovaptan and placebo, this nested design has 4 Holter extraction days and moxifloxacin is blinded to avoid unblinding of the placebo period. The moxifloxacin dosing day is the same number apart from the baseline as in the balovaptan periods to maintain the blind.

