5.3.1 Adverse Event Reporting Period

All AEs, whether reported by the subject or noted by study personnel, will be recorded in the subject's medical record and on the Adverse Event eCRF and source form.

After informed consent has been obtained but prior to initiation of study drug, only SAEs caused by a protocol-mandated intervention (e.g., invasive procedures such as biopsies, discontinuation of medications) should be reported (see Section [5.4.2](#) for instructions for reporting SAEs).

After initiation of study drug, all AEs will be reported until 21 days after the last dose of study drug.

Instructions for reporting AEs that occur after the AE reporting period are provided in Section [5.6](#).

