## 6.0 Study Design

This is a single-center, multiple-dose, randomized, double-blind, placebo-controlled, positive-controlled, twelve sequence 3-period cross-over study.

At the start of treatment period 1, at the end of Day -1, subjects will be randomized to one of the 12 treatment sequences comprised of 3 of the 4 treatments described in [6.2](#). All subjects will receive treatments A and B, half will receive treatment C, and the other half will receive treatment D. Each treatment period consists of 15 dosing days. Following each treatment period, subjects will undergo a washout period lasting a minimum of 13 and a maximum of 20 days from the last dose of study drug.

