**Treatment C (active control [400 mg moxifloxacin] on Day 2)**

Days 1-14: A single once daily oral dose of 5 tablets of matching placebo for balovaptan for 14 days.

Day 2: A single oral dose of 400 mg moxifloxacin capsule

Day 15: A single oral dose of a matching placebo capsule for moxifloxacin

[figure not shown]

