### **9.1.4 Descriptive Statistics**

Unless otherwise indicated, continuous variables will be summarized with the following descriptive statistics: n (number of observations), (arithmetic) mean, SD, min, median, and max.

Categorical data will be summarized with frequencies and percentages. Percentages by categories will be based on the number of subjects exposed within a treatment.

For categorical data the categories will be presented in the tables exactly as they appear in the CRF.

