## 9.2.2 Treatment/Subject Grouping

Label	Grouping
Study Drug	Balovaptan, matching placebo for balovaptan, moxifloxacin, matching placebo for moxifloxacin
Treatment	A: 10mg balovaptan B: 50mg balovaptan C: 400mg moxifloxacin on day 2 D: 400mg moxifloxacin on day 15
Dose Level	10mg balovaptan, 50mg balovaptan, 400mg moxifloxacin

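### SAP 17.1.1 summarises placebo-only adverse events in C and D under moxifloxacin-named treatments: about 20–28% of their attribution time, 37–52% in D

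*SAP*

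**What the plan says.** Every subject receives A (balovaptan 10 mg), B (balovaptan 50 mg) and one of C or D: "half will receive treatment C, and the other half will receive treatment D" (SAP 6.0). C and D are balovaptan-placebo regimens that each carry one moxifloxacin dose. For C this is "Day 2: A single oral dose of 400 mg moxifloxacin capsule"; for D it is on Day 15. Protocol 3.3.1.2 says moxifloxacin is given "in a nested cross-over fashion using a joint placebo/positive control period".

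The attribution rule in SAP 17.1.1 is "TEAEs occurring following dosing in a specific period but before dosing in the next period will be attributed to the treatment in that period". The TEAE summaries by preferred term, relationship and severity are then shown by treatment and overall. The treatment row of SAP 9.2.2 lists "C: 400mg moxifloxacin on day 2 D: 400mg moxifloxacin on day 15" and has no placebo level. SAP 9.1.4 sets the denominator: "Percentages by categories will be based on the number of subjects exposed within a treatment". C and D are pooled under a placebo label only in the echocardiogram summary (SAP 17.1.6).

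Two further passages fix the length of the attribution window. SAP 6.0 describes the washout as "lasting a minimum of 13 and a maximum of 20 days from the last dose of study drug", while Protocol 3.2 totals the three periods and two washouts at 80 to 94 days. The last period has no next dose, and 17.1.1 does not say where its attribution ends. Protocol 5.3.1 says "After initiation of study drug, all AEs will be reported until 21 days after the last dose of study drug".

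**The concern.** A TEAE on Day 5 of a D period arises ten days before that subject takes moxifloxacin, yet the rule places it in a column named for moxifloxacin. The same holds for Day 1 of C. Secondary objective 9 covers the safety of both balovaptan and moxifloxacin, so whether an event came before or after the capsule is informative for both drugs.

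As described, the summaries set A and B (about 56 subjects each) beside two columns of about 28, neither of them a placebo-only reference. No AE summary described in the SAP text shows which C or D events came before moxifloxacin. What is at stake is how the descriptive safety tables read. The primary QTc analysis, its alpha and its power are untouched.

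**Working it through.** **Inputs.** Dosing runs from Day 1 to Day 15 (SAP 6.0), so the last dose falls 14 days after the first. The capsule is on Day 2 in C and Day 15 in D, so 1 and 14 days of the window precede it. C and D are allocated 1:1. Washout is 13 to 20 days. AE reporting closes 21 days after the last dose (Protocol 5.3.1).

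**The plan's own figure.** 3 × 18 + 2 × 13 = 80 and 3 × 18 + 2 × 20 = 94 days, which matches Protocol 3.2. This total places the washout between discharge on Day 16 and the next check-in on Day -2. One Day 1 to the next Day 1 is then 18 + 13 = 31 to 18 + 20 = 38 days. Counting the same 13 to 20 days from the last dose to the next dose gives 14 + 13 = 27 to 14 + 20 = 34 days. The two readings differ, so both are carried forward.

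**Formulas.** With window W in days, the share before the capsule is 1/W in C, 14/W in D, and (1 + 14)/(2W) for C and D together.

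| Reading of the window | W (days) | C | D | C and D |
|---|---|---|---|---|
| Last dose to next dose | 27–34 | 3.7–2.9% | 51.9–41.2% | 27.8–22.1% |
| Last dose to Day -2 check-in, plus 2 days | 29–36 | 3.4–2.8% | 48.3–38.9% | 25.9–20.8% |
| As implied by the 80–94 day total | 31–38 | 3.2–2.6% | 45.2–36.8% | 24.2–19.7% |
| Period 3, closed at 21 days | 35 | 2.9% | 40.0% | 21.4% |

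C or D falls in Period 3 in 4 of the 12 sequences.

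**Subject-days.** With 28 subjects each in C and D, 28 × 1 + 28 × 14 = 420 subject-days precede the capsule. Totals run from 56 × 27 = 1512 to 56 × 38 = 2128, leaving 1092 to 1708 after it. So 72–80% of the pooled time follows moxifloxacin, and almost all of the placebo-only time (392 of 420 subject-days) lies in D.

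**Illustration for the D column (assumed, not from the documents).** Take a constant hazard, no drug effect, and a 15-day TEAE incidence p of 10, 20 or 30%. Incidence over d days is 1 − (1 − p)^(d/15).

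- d = 14: 9.4, 18.8, 28.3%, or 2.6, 5.3, 7.9 of 28 subjects with a TEAE before the capsule.
- d = 27: 17.3, 33.1, 47.4%, or 4.8, 9.3, 13.3 subjects counted in D.
- d = 38: 23.4, 43.2, 59.5%, or 6.6, 12.1, 16.7 subjects counted in D.

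On these assumptions, 54–60% (27 days) or 40–48% (38 days) of the D subjects counted would have a TEAE before moxifloxacin.

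**The case against.** The strongest reply is that this is a display choice, not an error. Protocol 6.5 plans AE summaries by study treatment, objective 9 speaks of the scheduled regimens, and 9.2.2 gives valid regimen names. No hypothesis test is planned (SAP 9.4.3). That stands, and it limits the point to an optional improvement.

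Second, the data permit reconstruction. AEs and exposure are listed by subject (SAP 17.1.1 and 15.0), study day is defined (SAP 9.2.3), and the numbers are small. This also stands. But listings do not change the summary tables, and under SAP 3.0 an analysis outside the plan must be identified as such in the study report.

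Third, the shells are approved with the SAP (9.5) but sit in a separate document (Appendix 5). They might contain a pooled column, so a reader should not infer that the outputs certainly lack one. They could not split events at the capsule without departing from the rule in 17.1.1.

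Fourth, causality assessment may help. The summary by relationship bears on single events but gives neither timing nor a placebo rate. Protocol 5.3.4 adds drug-by-drug causality after unblinding for combination therapy; whether that covers C and D is unclear.

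Two inferences are tempting and fail. One is that the SAP contradicts itself because it pools C and D as placebo for echocardiography. That assessment is on Day 13, before the capsule in D and 11 days after it in C, whereas the AE window runs through the capsule and the washout. The other is that the AE output titles in Appendix 4 show placebo was left out. None of those titles names any treatment, so they show nothing either way.

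**Conclusion.** The point holds as a cheap improvement to descriptive safety reporting. The stated rule puts placebo-only time under moxifloxacin-named treatments, and the AE text describes no placebo-only reference. About 20–28% of C and D attribution time precedes the capsule, 37–52% in D and 3–4% in C. These ranges cover every reading of the washout above, and Period 3 if it closes at 21 days. They assume equal numbers in C and D and full follow-up.

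A reader might take these as the fraction of events misplaced. The documents give no event rates, so only the time shares are established; the event illustration rests on its assumptions. A reader might also infer that pooling C and D would supply the missing placebo rate. It would not, because most of the pooled time follows moxifloxacin. The split at the capsule does the work.

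**What to change.** In SAP 17.1.1:

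1. Keep the A, B, C and D regimen columns. Within C and D, also summarise TEAEs by onset before the moxifloxacin capsule (placebo only) versus on or after it, with subject-days of exposure for each part.
2. Name one rule for missing start times on the capsule day. Section 17.1.1 sets them to 00:01 for onset and duration but to one minute after dosing for treatment assignment. The first would put the event before the capsule, the second after it. State that the split follows the treatment-assignment rule. This is workable because on Day 2 the capsule directly follows the placebo tablets (Protocol 4.3.2.2) and on Day 15 it is the only dose. A missing start date stays unattributed, as now.
3. Count a subject once per term within each part.
4. State that attribution in the last period ends at the 21-day AE reporting limit.
5. Optionally add a C plus D column over the full period. If shown, label it 'Placebo with single-dose moxifloxacin', not 'Placebo'.

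The washout wording in SAP 6.0 and the 80–94 day total in Protocol 3.2 should be reconciled so that the exposure days have one definition.

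The cost is a paragraph of SAP text, one variable derived from dose and onset times already collected, and a few table rows or columns. The downside is unequal exposure (420 against 1092–1708 subject-days). The percentages for each part must be read with their exposure days and not set directly against A and B.

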### **17.1.2 Serious Adverse Events**

A listing of SAEs will be provided by subject.

### **17.1.3 Laboratory Data**

Clinical laboratory data will be presented using units from the study data tabulation model (SDTM) Controlled Terminology.

Descriptive statistics summarizing continuous laboratory results of clinical chemistry, hematology, urinalysis, and myocyte by treatment and visit will be provided.

All laboratory data will be listed by subject, including laboratory variables not listed in the protocol. A separate listing of out-of-range values will also be provided. Normal ranges will be used directly from the clinical laboratory and will be included in the listings for reference.

### **17.1.4 Vital Signs**

Descriptive statistics summarizing vital signs by treatment and scheduled time will be provided.

All vital signs will be listed by subject, including orthostatic challenge testing taken at supine and standing positions.

Orthostatic change will be calculated for orthostatic challenge testing results for Systolic Blood Pressure, Diastolic Blood Pressure, and Pulse Rate as: Orthostatic Vital Sign = Standing Vital Sign – Supine/Sitting Vital Sign.

### **17.1.5 12-Lead Safety Electrocardiograms**

Descriptive statistics summarizing ECG parameters by treatment and visit will be provided.

All ECG parameters and the corresponding abnormalities will be listed by subject.

### **17.1.6 Echocardiograms**

Descriptive statistics summarizing echocardiogram parameters, changes from baseline, and changes from baseline relative to placebo by treatment and visit will be provided. Treatments C and D will be pooled for this summary and displayed as "Placebo." Change from baseline relative to placebo will be calculated as change from baseline for the placebo period minus the change from baseline for treatment A and B periods.

---

All ECG parameters and the corresponding categorical indicators will be listed by subject.

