6.7.5 Assay Sensitivity

In order to confirm that the assay is sufficiently sensitivity to detect an effect, the following statistical hypothesis is tested for values recorded at the three pre-defined post-dose time points (1.25, 2.5, and 4 hours):

$$H_0: \cap \{\mu_{M(i)} - \mu_{P(i)}\} \leq 5, i = 1,2,3$$

$$H_1: \cup \{\mu_{M(i)} - \mu_{P(i)}\} > 5, i = 1,2,3$$

where $\mu_{M(i)}$ and $\mu_{P(i)}$ are the LS mean of Δ QTcF for moxifloxacin and placebo at time point i , respectively.

The analysis to show assay sensitivity will be based on the change-from-baseline post-dosing QTcF of moxifloxacin. The same model will be used as described for the primary analysis. For the 3 predefined time points (1.25, 2.5, and 4 hours post-dosing), the contrast in treatment $\Delta\Delta$ QTcF = “moxifloxacin - placebo” will be tested against the 1-sided null hypothesis $\Delta\Delta$ QTcF \leq 5 ms on the 5% level. Multiplicity will be controlled by using a Hochberg procedure.¹⁰ If after this procedure, the LS mean of $\Delta\Delta$ QTcF is significantly larger than 5 ms for at least 1 time point of these 3 time points, assay sensitivity will be considered shown. In addition, 2-sided 90% CIs will be obtained for the contrast at all time points and used in the figures.

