6.7.7 Concentration-QTc Analysis (Secondary Analysis)

The concentration-QTc analysis will be based on placebo-corrected change-from-baseline QTcF ($\Delta\Delta\text{QTcF}$). That is, for the placebo adjustment, the individual ΔQTcF for placebo calculated at a specific time point is subtracted from ΔQTcF for the same subject on balovaptan at the same time point to generate $\Delta\Delta\text{QTcF}$. The relationship between plasma concentrations of balovaptan and its metabolites (M2 [as appropriate] and M3) and $\Delta\Delta\text{QTcF}$ will be investigated by linear mixed-effects modeling.

A full model will include $\Delta\Delta\text{QTcF}$ as the dependent variable, time-matched plasma concentrations of each analyte (balovaptan, M2 [as appropriate] and M3) as the covariates, centered baseline QTcF as an additional covariate (i.e., baseline QTcF for individual subject at each post-dose time point subtracting the population mean baseline QTcF for all subjects), and subject as a random effect for both intercept and slopes, when applicable. Assay sensitivity may also be evaluated by a concentration-QTc analysis of the effect on $\Delta\Delta\text{QTcF}$ of moxifloxacin using a similar model as the above one.

The following model selection procedure among the full model and reduced models from possible first order combinations (without quadratic and interaction terms) among the three analytes (including models with only one analyte and with any two analytes) will be conducted by using Akaike Information Criterion (AIC) and the t-value for the intercept estimator.⁵ The selection will start from the full model and remove the analyte with the least significant slope from the model until only one analyte is left to evaluate the most appropriate model(s). Note that a significant intercept is not biologically plausible and therefore indicates model misfit. The selection of the final models will be performed among those models with an absolute t-value for the intercept estimate < 1.95 . Nonlinear models (Emax model) will be included in this set only if the test for linearity indicates non-linearity. Among these models, the model with the smallest AIC will be selected as primary. If none of the models qualify according to the condition on the t-value for the intercept estimator, non-linear models will be considered.

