6.8 TT-DOPPLER ECHOCARDIOGRAM

Results from TT-Doppler echocardiogram at each time point will be listed by subject for each time point. Descriptive summary statistics for each parameter by time point as well as its change from baseline and change relative to placebo will be provided and illustrated by plots by individual subject and treatment cohorts. A more detail discussion of statistics for this parameter will be provided in the SAP to be completed prior to database lock.

Categorical analysis will refer N subjects per treatment with mPAP exceeding 25 mm Hg.

Additional exploratory analyses may be made post-hoc.

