### 5.3.3 Exploratory Endpoints

1. TT-Doppler echocardiography: pulmonary artery acceleration time (PAAT), right ventricular outflow tract - velocity time integral (RVOT-VTI) and derived mean pulmonary arterial pressure as change to baseline relative to placebo treatment.
2. TT-Doppler-echocardiography: left ventricular ejection fraction (LVEF) and additional secondary TT-Doppler-echocardiography parameters of left and right heart.
3. ABPM: mean diastolic and systolic blood pressure (daytime and nighttime mean).
  - a. Heart rate will be analyzed as derived from Holter ECG.
    - i. Heart rate as derived from ABPM and/or Holter ECG may be explored against fluctuations in blood pressure measured by ABPM (if warranted).

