## 7.0 Overview of Planned Analysis

### 7.1 Changes from Protocol

There are no changes from the protocol.

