## 9.2.3 Common Variable Derivations

Variable	Data Type	Definition/Calculation
Change from baseline	All	Post-dose Observation minus baseline Observation within period
Change from baseline relative to placebo	TT-Doppler Echocardiogram Parameters	Change from baseline for the treatment C or D period minus the change from base for the treatment A or B period
Analysis Study Day (Prior to first Dose)	All	Date of Measurement minus Dose Date
Analysis Study Day (Post first Dose)	All	Date of Measurement minus Dose Date +1

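### The SAP computes the echocardiographic change from baseline relative to placebo as placebo minus balovaptan, which reverses the sign of the reported effect

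*SAP*

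**What the plan says.** The first exploratory endpoint in SAP 5.3.3 covers PAAT, RVOT-VTI and "derived mean pulmonary arterial pressure as change to baseline relative to placebo treatment".

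SAP 9.2.3 derives change from baseline as "Post-dose Observation minus baseline Observation within period". For the echo parameters it then derives the placebo-relative change as "Change from baseline for the treatment C or D period minus the change from base for the treatment A or B period". SAP 17.1.6 pools treatments C and D as placebo and repeats the order of subtraction: "change from baseline for the placebo period minus the change from baseline for treatment A and B periods".

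The protocol gives no order of subtraction for echo. Protocol 6.8 promises a descriptive summary of change relative to placebo and defers the rest: "A more detail discussion of statistics for this parameter will be provided in the SAP". SAP 3.0 says that the SAP supersedes the protocol's statistical text, so the SAP formula is the only operative definition. SAP 7.1 states "There are no changes from the protocol", and nothing in the SAP comments on the direction chosen.

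Table 14.3.8 is the only echo summary table in SAP Appendix 4. Its title names the placebo-relative change without a direction.

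**The concern.** A change expressed relative to placebo takes placebo as the reference, so placebo should be the term subtracted. The SAP subtracts balovaptan. A reader who takes the label in its usual sense would read a balovaptan-related rise in a continuous echo parameter as a fall, and a fall as a rise.

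Direction is what this assessment is for. Protocol 3.3.3 explains that vasopressin lowered pulmonary pressure through V1a receptors in animals. Balovaptan blocks that receptor, and the study looks for any effect on pulmonary pressure and on the right and left heart. The same study report would also carry placebo-corrected QTcF values with the opposite sign convention.

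The order appears identically in two sections, one of them the derivation table, so it would be programmed as written. Checking the output against the SAP would confirm the reversed values. Echo is also not among the datasets that SAP 9.2.4.1 classes as critical.

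**Working it through.** The plan states no figure for this quantity, so there is none to reproduce. The check has three parts.

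**1. Direction of the placebo contrasts**

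| Place | Quantity | Order |
|---|---|---|
| Protocol 6.7.3 | Primary QTcF hypothesis | Balovaptan mean minus placebo mean |
| Protocol 6.7.5 | Assay sensitivity | "moxifloxacin - placebo" |
| Protocol 6.7.7 | Concentration-QTc: the individual change "for placebo calculated at a specific time point is subtracted from" the same subject's change on balovaptan | Balovaptan minus placebo |
| SAP 9.2.3 and 17.1.6 | Echo, relative to placebo | Placebo minus balovaptan |

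**2. Effect on the numbers**

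Let d_B = post-dose minus baseline in a balovaptan period, and d_P = the same difference in the subject's C or D period.

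- SAP rule: d_P - d_B
- Active minus placebo: d_B - d_P
- Hence the SAP rule = -1 x (active minus placebo).

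One subject, with values assumed for illustration: LVEF goes from 60 to 57 on treatment B, so d_B = -3. It stays at 60 in the placebo period, so d_P = 0.

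- SAP rule: 0 - (-3) = +3
- Active minus placebo: -3 - 0 = -3

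Five subjects, also assumed: balovaptan changes 4, 2, 7, -1, 3 and placebo changes 1, 0, 2, -2, 1. The SAP differences are -3, -2, -5, -1, -2.

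| Statistic | SAP rule | Active minus placebo |
|---|---|---|
| n | 5 | 5 |
| Mean | -2.6 | +2.6 |
| Median | -2.0 | +2.0 |
| Minimum | -5.0 | +1.0 |
| Maximum | -1.0 | +5.0 |
| SD | 1.52 | 1.52 |

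Mean and median change sign. Minimum and maximum change sign and swap places. The n and SD do not change, so nothing in the table would look odd.

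**3. How much of the output is affected**

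SAP 17.1 lists 19 echo entries. Four are valve findings (tricuspid and pulmonary regurgitation, aortic insufficiency, mitral regurgitation) and one is the count of subjects with mPAP above 25 mm Hg.

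- 19 - 4 - 1 = 14 entries, continuous on a plain reading: PAAT, RVOT-VTI, IVC diameter, right atrial size, RIMP, RV end-systolic pressure, RV end-diastolic pressure, systolic PAP, diastolic PAP, RV wall thickness, RV size, LVEF, LV wall thickness and E/E'.
- Each period has one on-treatment echo (Day 13, Protocol 4.5.7), and there are two balovaptan doses: 14 x 2 = 28 placebo-relative contrasts.

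Derived mean PAP would be added if it is tabulated as a continuous value, as the endpoint in SAP 5.3.3 requires. SAP 17.1 names mPAP only as the count, so this cannot be confirmed.

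**The case against.** The strongest reply is that no rule is broken. The SAP states its direction openly and consistently, the protocol sets none for echo, and the QTcF contrasts belong to a separate cardiodynamic SAP (SAP 5.0). On this view the sign is an unusual convention. It is true that the protocol's silence means SAP 7.1 is not false on this point; it shows only that the reversal is not flagged. But the label still makes placebo the reference while the formula makes balovaptan the reference, and the results of both SAPs describe the same study.

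The shells, which SAP 9.5 treats as part of the approved plan, are in a separate document (Appendix 5) and might state the direction in a header or footnote. That cannot be excluded. Nothing in the protocol or SAP text does so.

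The reversal can also be detected from planned output. SAP 17.1.6 provides changes from baseline by treatment with placebo displayed, and Listing 16.2.11 gives subject results. In the LVEF example a careful reader would see -3 on B and 0 on placebo beside the +3. This limits the harm but does not make the +3 a sound summary.

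The count of 28 multiplies one definition by a parameter list. Systolic and diastolic PAP are estimated only where regurgitation is present (Protocol 4.5.7), so paired values for these may be few. The figure is therefore the scope of the definition; the number of populated cells may be smaller.

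Finally, no decision uses this sign. No formal testing is planned (SAP 9.4.3), and the subject-level safety review in Protocol 5.1.2.5 looks at individual findings. This bears on the weight of the point and leaves the reversal as it is.

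**Conclusion.** The concern holds. As written, SAP 9.2.3 and 17.1.6 produce the balovaptan effect multiplied by -1 under a label that implies the opposite order. This reaches 14 continuous parameters, or 28 contrasts over two doses, in Table 14.3.8; the absolute size of each effect and its SD are correct. Raw values, within-treatment changes, listings, valve categories and the mPAP count are unaffected, and so are all error rates and the QT conclusion.

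The conclusion rests on reading relative to placebo in its usual sense, which the protocol's QTcF contrasts support, and on the unseen shells not stating the direction. The count rests on the variable names in SAP 17.1. The point should be fixed because these are reported cardiac safety statistics and the correction is small.

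**What to change.** In SAP 9.2.3 and 17.1.6, define the echo quantity as the change from baseline in the treatment A (or B) period minus the change from baseline in the same subject's placebo period (C or D). Align the shell and program for Table 14.3.8, and state balovaptan minus placebo in its title or a footnote.

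Keeping the present formula and labelling the table placebo minus balovaptan would remove the ambiguity, but the echo results would still run opposite to the QTcF results, so redefinition is preferable.

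The cost is two SAP sentences and the alignment of one table's shell and code. No new data are needed.
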